15.5. VITAL SIGNS

The following Vital Signs measurements will be reported for this study:

- Systolic Blood Pressure (SBP) (mmHg)
- Diastolic Blood Pressure (DBP) (mmHg)
- Systolic Blood Pressure(mmHg) (SBP) (Upright Position)
- Diastolic Blood Pressure(mmHg) (DBP) (Upright Position)
- Respiratory Rate (RR) (resp/min)
- Heart Rate (HR) (bpm)
- Temperature (°C)

Document: Statistical Analysis Plan

Author: [name]

Version Number: 1.1

Version Date: 18Jan2023

Template No.: CS_TP_BS016 Revision 5

Reference: CS_WI_BS005

Effective Date: 01Apr2018

- Weight (kg)
- Height (cm)

The following summaries will be provided for vital signs data:

- Actual and change from baseline by visit
- Incidence Markedly Abnormal Values of vital signs:
 - SBP (mmHg) Low is defined as observed value less or equal to 90 and change from baseline less or equal to -20.
 - SBP (mmHg) High is defined as observed value greater or equal to 180 and change from baseline greater or equal to 20.
 - DBP (mmHg) Low is defined as observed value less or equal to 50 and change from baseline less or equal to -15.
 - DBP (mmHg) High is defined as observed value greater or equal to 105 and change from baseline greater or equal to 15.
 - HR (Bpm) Low is defined as observed value less or equal to 50 and change from baseline less or equal to -15.
 - HR (Bpm) High is defined as observed value greater or equal to 120 and change from baseline greater or equal to 15.
 - Temperature (°C) High is defined as observed value greater or equal to 38.3 and change from baseline greater or equal to 1.1.
 - Weight (kg) Low is defined as percentage change from baseline less or equal to -7.0%.
 - Weight (kg) High is defined as percentage change from baseline greater or equal to 7.0%.
- Listing of vital signs

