 - For subjects who cannot continue participating in the study for any reason, the investigator should try to complete evaluation for them during last dose/early termination visit.
- 2. Medical history survey includes a history of smoking and alcohol drinking and drug abuse. Family history should include a family history of colon cancer and a family history of premature coronary heart disease. The medical history within 3 years before screening is necessarily recorded (the records of history of major diseases and history of surgery are not subject to this limitation.)
- 3. Patients can be enrolled in the study if it is evidenced that previous TB was treated successfully and Quantiferon or Quantiferon Plus test result at screening is negative. If Quantiferon or Quantiferon Plus test result is indeterminate at screening, it could be retested during screening period. If Quantiferon or Quantiferon Plus retest result is indeterminate, the subject should not participate in the study. If Quantiferon or Quantiferon Plus retest result is negative, the subject can be enrolled in the study.
- 4. Chest X-ray taken within 3 months prior to screening will be accepted. If no chest X-ray are taken within 3 months before screening, a chest X-ray will be performed at the screening visit. Subjects who prematurely terminated from the study need to undergo chest radiography at the last dose/early termination visit.
- 5. On Day 1, 2, 5 and 8, 12-lead ECG will be performed within 2 hours before dosing and at 4, 6 hours after dosing. At other follow-up time points, 12-lead ECG tests will be performed at 4 hours after dosing. Time window for 12-lead ECG tests is ±0.5 hours.
- 6. On Day 0, 1, 5 and 8, 24 ± 0.5 hour continuous Holter monitoring will be performed from 30 min ± 10 min before dosing (the same time point as day 0).
- 7. Vital signs include the heart rate, blood pressure, body temperature and respiratory rate. On Day 1, 2, 5 and 8, vital signs are measured before dosing and at 1, 2, 3, 4, 5 and 6 hours (±10 minutes) after dosing. At other scheduled visits, vital signs will be measured before dosing.

Confidential

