- Laboratory: absolute value and change from baseline by visit of hematology, biochemistry, fasting lipids, coagulation, and urinalysis; shift from baseline to worst post-baseline common terminology criteria for adverse events (CTCAE) grade for hematology, biochemistry, fasting lipids, and coagulation; abnormalities in hematology and liver function test. The above summary tables are in Stage 1 as well as their reference listings.
- 12-Lead ECG: absolute value and change from baseline by visit of ECG; shift from baseline to worst post-baseline ECG overall assessment; abnormalities in QT internal and QTcF; shift from baseline to maximum post baseline value and maximum increase from baseline in Stage 1
- Other safety findings: vital signs (VS) part, including absolute value and change from baseline by visit and incidence of markedly abnormal values, and shift from baseline to worst post-baseline overall assessment; pulmonary function test data's absolute value and change

Document: Statistical Analysis Plan

Author: [name]

Version Number: 1.1

Version Date: 18Jan2023

Template No.: CS_TP_BS016 Revision 5

Reference: CS_WI_BS005

Effective Date: 01Apr2018

from baseline; ophthalmologic examination part, including overall assessment by visit and change from baseline; optical coherence tomography part, including overall assessment by visit and change from baseline; dermatologic examination part, including overall assessment by visit and change from baseline in Stage 1.

- Concomitant medications and procedures (details in section 11) in Stage 1.

If a decision is made to perform the primary or main analysis, in order to maintain study integrity with respect to the follow-up visits, safety visits and analyses, a Blind Maintenance Plan will be written. This plan will clearly identify the team (including the statistician) that will perform the primary or main analysis and all related activities, restrict other clinical team members and other Sponsor personnel from access to individual subject treatment allocation and site level analysis results, and ensure that the dedicated team will not participate in the data decisions for the following analyses. However, the dedicated team can participate in the analysis following the final database lock.

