6.3. RETESTS, UNSCHEDULED VISITS

In general, for by-visit summaries, data recorded at the nominal visit will be presented. Unscheduled measurements will not be included in by-visit summaries but will contribute to the minimum, maximum, best or worst case value where required (e.g. shift table).

Unless otherwise specified, in the case there are more than one records in the same visit, the latest available measurement for that visit will be used for by-visit summaries.

Listings will include scheduled, unscheduled, retest data.

Document: Statistical Analysis Plan

Author: [name]

Version Number: 1.1

Version Date: 18Jan2023

Template No.: CS_TP_BS016 Revision 5

Reference: CS_WI_BS005

Effective Date: 01Apr2018

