15.4. ECG EVALUATIONS

The following ECG parameters will be reported for this study:

- Heart Rate (bpm)
- PR Interval (msec)
- RR Interval (msec)
- QRS Interval (msec)
- QT Interval (msec)
- QTcF Interval (msec)
- Overall assessment of ECG (Investigator's judgment):
 - Normal
 - Abnormal, Not Clinically Significant (NCS)
 - Abnormal, Clinically Significant (CS)
 - Not Evaluable

The following summaries will be provided for ECG data:

- Actual value and change from baseline by visit
- Shift from baseline to worst post baseline for overall evaluation
- Incidence of subjects with abnormalities for QT Internal/QTcF by visit
- Shift from baseline according to post-baseline maximum value category for QT Interval

Document: Statistical Analysis Plan

Author: [name]

Version Number: 1.1

Version Date: 18Jan2023

Template No.: CS_TP_BS016 Revision 5

Reference: CS_WI_BS005

Effective Date: 01Apr2018

and QTcF

- Shift from baseline according to post-baseline maximum increase category for QT Interval and QTcF
- Listing of ECG
- Listing of Holter ECG

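### Heart rate on titration days is tabulated only by visit, with no post-dose time-point or minimum summary, and the HR Low row omits some readings at the protocol's own bradycardia levels

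*SAP*

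**What the plan says.** **Collection.** Footnote 7 to Protocol Table 2 (stage 1) states: "On Day 1, 2, 5 and 8, vital signs are measured before dosing and at 1, 2, 3, 4, 5 and 6 hours". Footnote 5 puts the ECGs on those days before dosing and at 4 and 6 hours. The footnotes to Table 4 repeat both schedules for the sub-study 2 titration. Protocol 3.4.4 places the dose-dependent heart-rate fall at 2-4 hours after dosing.

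**By-visit tables.** The continuous summary of vital signs in SAP 15.5 is "Actual and change from baseline by visit". SAP 15.4 treats ECG parameters, heart rate among them, the same way. SAP 6.3 says that, unless otherwise specified, when a visit holds more than one record "the latest available measurement for that visit will be used for by-visit summaries". Neither 15.4 nor 15.5 specifies otherwise.

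**Worst-case outputs.** SAP 15.4 plans "Shift from baseline according to post-baseline maximum increase category for QT Interval and QTcF", a matching maximum-value shift for the same two intervals, and "Shift from baseline to worst post baseline for overall evaluation". For vital signs, SAP 4.2 adds "shift from baseline to worst post-baseline overall assessment", which 15.5 does not repeat. None of these covers heart rate in bpm. Holter data appear only as "Listing of Holter ECG".

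**Categorical row.** SAP 15.5: "HR (Bpm) Low is defined as observed value less or equal to 50 and change from baseline less or equal to -15". The protocol's own levels are absolute: below 50 bpm awake for a bradycardia AE (8.1.1) and 45 bpm or below for an AESI (8.3).

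**Baseline.** Protocol 7.3.2 uses the lowest pre-dose value, chosen by reference to systolic pressure. SAP 6.2 uses the last non-missing value before first treatment.

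**The concern.** Slowing of the heart is the known dose-related effect of this drug class and a stated reason for titration and intensive cardiac monitoring. Vital signs and ECG findings belong to a secondary safety endpoint. Yet the SAP text specifies no table showing, by arm, how far measured heart rate falls at the time the fall is expected. QT and QTcF get maximum-change summaries and heart rate gets no equivalent.

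The only categorical heart-rate row for slowing joins an absolute level to a change from baseline. It is therefore least sensitive in subjects who start low, and Protocol 7.5 asks clinicians to watch those subjects. For some of them, counts at the protocol's own levels would rest entirely on what investigators chose to report.

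**Working it through.** The plan states no figure to reproduce here. The check applies its rules to its own schedule and thresholds.

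**1. Which reading enters the by-visit table**

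- Vital signs on a titration day: pre-dose, 1, 2, 3, 4, 5, 6 h. The latest is 6 h, so 1 of 6 post-dose readings is shown.
- ECG: pre-dose, 4, 6 h. The latest is 6 h, so 1 of 2 post-dose readings is shown.
- Expected fall: 2-4 h. The readings at 2, 3 and 4 h and the 4 h ECG drop out of the by-visit summaries.

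Day 2 has no visit number in Protocol Table 2, although Protocol 8.6 reports the fall on the first two days of dosing. The documents do not say where Day 2 readings are stored. If they sat under the Day 1 visit, the literal rule would keep the Day 2 6 h value and lose Day 1.

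**2. Which readings HR Low counts**

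For baseline b and reading v in whole bpm, the row counts v only if v ≤ 50 and v − b ≤ −15, that is v ≤ min(50, b − 15).

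- At the AESI level (v ≤ 45), readings from b − 14 to 45 are not counted. There are 60 − b of them, reaching zero at b = 60.
- At the AE level (v < 50, so v ≤ 49), readings from b − 14 to 49 are not counted. There are 64 − b of them, reaching zero at b = 64.

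| Baseline | Highest reading counted | ≤45 not counted | <50 not counted |
|---|---|---|---|
| 50 | 35 | 36-45 (10) | 36-49 (14) |
| 54 | 39 | 40-45 (6) | 40-49 (10) |
| 55 | 40 | 41-45 (5) | 41-49 (9) |
| 56 | 41 | 42-45 (4) | 42-49 (8) |
| 57 | 42 | 43-45 (3) | 43-49 (7) |
| 58 | 43 | 44-45 (2) | 44-49 (6) |
| 59 | 44 | 45 (1) | 45-49 (5) |
| 60 | 45 | none | 46-49 (4) |
| 63 | 48 | none | 49 (1) |
| 64 | 49 | none | none |

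Exclusion criterion 17j removes subjects below 55 bpm at the screening visit. The SAP baseline can be a later value, so 55 is not a floor for b; the rows for 50 and 54 show what follows if it is lower.

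Every omitted reading is a fall of at most 14 bpm. As a check, the phase I subject in Protocol 3.4.4 had a baseline of 55 and a low of 33: 33 ≤ 40, a fall of 22, so counted. The gap concerns smaller falls from low starting rates.

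**3. Baseline**

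The change condition depends on b, and Protocol 7.3.2 and SAP 6.2 define b differently. Because the protocol's choice is tied to systolic pressure, the selected heart rate need not be the lowest one, and the text does not settle which way the counts would move.

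**The case against.** The best counter-argument is that SAP 6.3 is headed as a rule for retests and unscheduled visits and yields to other specifications. A programmer might well not apply it to scheduled serial readings. SAP 6.2 does separate pre-dose from post-dose measurements, and Appendix 1 sends layouts to table shells that may show time points. This stands as a limit: the 6 h result holds only on a literal reading. But the sentence on several records in one visit is general, and nothing in 15.4 or 15.5 overrides it.

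Nor is 6 h an idle time. Tmax is 4-6 h (Protocol 3.4.3), and Tables 7 and 8 use 6 h to decide on further monitoring. A 6 h summary is useful, but it does not describe the fall at 2-4 h.

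Readings at the protocol levels have another route. Protocol 8.1.1 and 8.3 make them reportable, and the SAP tabulates TEAEs and AESIs. That is true, but those tables depend on site reporting and carry no bpm.

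The two-part form is also used for blood pressure and temperature, so it is a convention rather than a slip, and HR Low may already draw on all time points. Both points are fair. The 15 bpm condition still excludes the readings above, and a yes/no count shows no size of fall.

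Finally, no prevalence is given. None can be derived from the documents.

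**Conclusion.** The concern holds. SAP 15.4 and 15.5 specify no time-point, minimum or maximum-decrease summary of heart rate on titration days. Applied literally, SAP 6.3 leaves the 6 h reading in the by-visit tables. HR Low omits some readings of 45 or below at baselines up to 59, and some below 50 at baselines up to 63.

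This should be corrected, but it does not touch the primary efficacy analysis. Confidence is moderate, because the table shells, the DMC SAP and the Holter operating document are not among the documents and could fill part of the gap. The arithmetic assumes whole-bpm readings and nothing about their distribution. The baseline conflict is real, with undetermined effect.

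**What to change.** In SAP 15.4 and 15.5:

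- Exempt the titration days of stage 1 and sub-study 2 from the latest-record rule in 6.3.
- Summarise heart rate by nominal time point, and by post-dose minimum and maximum decrease, for each arm in stage 1 and for the single open-label arm in sub-study 2.
- State where Day 2 readings are shown.
- Keep HR Low and add incidence rows for any post-dose heart rate below 50 bpm and for 45 bpm or below. These are the protocol's existing reporting levels; no new threshold is introduced.
- Reconcile the heart-rate baseline in Protocol 7.3.2 with SAP 6.2, and state in 15.5 which one is used.

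The cost is SAP wording and a few extra descriptive safety outputs. The protocol already collects the readings.

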15.6. PHYSICAL EXAMINATION

The following summaries will be provided for physical examination results:

- Overall assessment of physical examination
- Listing of physical examination

The following specific assessments will be conducted: neck/thyroid, chest/lung, heart, lymph, nodes, abdomen, nervous system, and other (if applicable). Each measurement will be categorized as normal/abnormal, NCS/abnormal, CS/NE. Nervous System Physical Examination result will be also summarized by symptoms.

15.7. OTHER SAFETY ASSESSMENTS

15.7.1. PULMONARY FUNCTION TEST

The following pulmonary function test measurements will be reported for this study:

- FEV1 Results
- FEV1 Predicted Results
- FEV1% Predicted Results
- FVC Results
- FVC Predicted Results
- FVC % Predicted Results
- DLCO Results
- DLCO Predicted Results
- DLCO % Predicted Results

The following summaries will be provided for pulmonary function test data:

- Actual value, change, percent change and change in percent predicted from baseline by visit
- PFT test results will also be listed.

Document: Statistical Analysis Plan

Author: [name]

Version Number: 1.1

Version Date: 18Jan2023

Template No.: CS_TP_BS016 Revision 5

Reference: CS_WI_BS005

Effective Date: 01Apr2018

15.7.2. OPHTHALMOLOGIC EXAMINATION

The following summaries will be provided for ophthalmologic examination data:

- Ophthalmologic examination result by visit
- Shift from baseline to worst post baseline
- Listing of ophthalmologic examination data

15.7.3. OPTICAL COHERENCE TOMOGRAPHY

The following summaries will be provided for optical coherence tomography data:

- Optical coherence tomography result by visit
- Shift from baseline to worst post baseline
- Listing of optical coherence tomography data

15.7.4. DERMATOLOGIC EXAMINATION

The following summaries will be provided for dermatologic examination data:

- Dermatologic examination result by visit
- Shift from baseline to worst post baseline
- Listing of dermatologic examination data

15.7.5. PREGNANCY TEST

Pregnancy test data will only be listed.

15.7.6. CHEST IMAGING EXAMINATION

Chest imaging examination data will only be listed.

Document: Statistical Analysis Plan

Author: [name]

Version Number: 1.1

Version Date: 18Jan2023

Template No.: CS_TP_BS016 Revision 5

Reference: CS_WI_BS005

Effective Date: 01Apr2018

APPENDIX 1. PROGRAMMING CONVENTIONS FOR OUTPUTS

IQVIA OUTPUT CONVENTIONS

Outputs will be presented according to the Shells.

SPELLING FORMAT

English US.

PRESENTATION OF TREATMENT GROUPS

For outputs, treatment groups will be represented as follows and in that order:

Treatment Group	For Tables and Graphs	For Listings (include if different to tables)
0.1 mg	0.1 mg	
0.2 mg	0.2 mg	
Placebo	Placebo	

PRESENTATION OF VISITS

For outputs, visits will be represented as follows and in that order:

Long Name (default)	Short Name
Stage 1	
Screening (Visit 1)	Scr (V1)
Baseline (Visit 2)	BL (V2)

Document: Statistical Analysis Plan

Author: [name]

Version Number: 1.1

Version Date: 18Jan2023

Template No.: CS_TP_BS016 Revision 5

Reference: CS_WI_BS005

Effective Date: 01Apr2018

Long Name (default)	Short Name
Week 1 day 1 (Visit 3)	W1D1 (V3)
Week 1 day 5 (Visit 4)	W1D5 (V4)
...	...
Week 16 (Visit 12)	W16 (V12)
Stage 2 sub-study 1	
Week 13 (Visit 12)	W13 (V12)
Week 18 (Visit 13)	W18 (V13)
Week 24 (Visit 14)	W24 (V14)
Week 32 (Visit 15)	W32 (V15)
Week 40 (Visit 16)	W40 (V16)
Week 48 (Visit 17)	W48 (V17)
Week 52 (Visit 18)	W52 (V18)
Stage 2 sub-study 2	
Week 13 (Visit 12)	W13 (V12)
Week 13 day 1 (Visit 13)	W13D1 (V13)
Week 13 day 5 (Visit 14)	W13D5 (V14)
Week 14 (Visit 15)	W14(V15)
Week 16 (Visit 16)	W16(V16)
Week 24 (Visit 17)	W24(V17)
Week 32 (Visit 18)	W32 (V18)
Week 40 (Visit 19)	W40 (V19)
Week 48 (Visit 20)	W48 (V20)
Week 52 (Visit 21)	W52 (V21)

Document: Statistical Analysis Plan

Author: [name]

Version Number: 1.1

Version Date: 18Jan2023

Template No.: CS_TP_BS016 Revision 5

Reference: CS_WI_BS005

Effective Date: 01Apr2018

LISTINGS WILL BE ORDERED BY THE FOLLOWING (UNLESS OTHERWISE INDICATED IN THE TEMPLATE):

- Randomized treatment group (or treatment received if it's a safety output), first by active dose [by ascending dose group] and then control/ placebo.
- center-subject ID,
- date (where applicable),
- For listings where non-randomized subjects are included, these will appear in a category after the randomized treatment groups labeled 'Not Randomized'.

Document: Statistical Analysis Plan

Author: [name]

Version Number: 1.1

Version Date: 18Jan2023

Template No.: CS_TP_BS016 Revision 5

Reference: CS_WI_BS005

Effective Date: 01Apr2018

APPENDIX 2. LISTING OF EFFICACY PARAMETERS AND STUDY POPULATIONS ANALYSED IN STAGE 1

Efficacy Parameters	Response Analyzed	Comparison Groups			Visit	Study Populations Analyzed	Imputation Method
		Group1	Group2	Statistical Method			
Primary Endpoint (Stage 1)							
Adapted Mayo Score	Change from Baseline	0.2mg QD	Placebo	ANCOVA	Week 12	FAS, mFAS, PPS	MCMC MI, LOCF
Secondary Endpoints (Stage 1)							
Adapted Mayo Score	Change from Baseline	0.1mg QD	Placebo	ANCOVA	Week 12	FAS, mFAS, PPS	MCMC MI, LOCF
Complete Mayo Score	Change from Baseline	0.2mg QD	Placebo	ANCOVA	Week 12	FAS, mFAS, PPS	MCMC MI, LOCF
Complete Mayo Score	Change from Baseline	0.1mg QD	Placebo	ANCOVA	Week 12	FAS, mFAS, PPS	MCMC MI, LOCF
Adapted Mayo Score	Clinical Response Rate	0.2mg QD	Placebo	ANCOVA	Week 12	FAS, mFAS, PPS	NRI
Adapted Mayo Score	Clinical Response Rate	0.1mg QD	Placebo	ANCOVA	Week 12	FAS, mFAS, PPS	NRI
Complete Mayo Score	Clinical Response Rate	0.2mg QD	Placebo	ANCOVA	Week 12	FAS, mFAS, PPS	NRI
Complete Mayo Score	Clinical Response Rate	0.1mg QD	Placebo	ANCOVA	Week 12	FAS, mFAS, PPS	NRI
Adapted Mayo Score	Clinical Remission Rate	0.2mg QD	Placebo	ANCOVA	Week 12	FAS, mFAS, PPS	NRI

Document: Statistical Analysis Plan

Author: [name]

Version Number: 1.1

Version Date: 18Jan2023

Template No.: CS_TP_BS016 Revision 5

Reference: CS_WI_BS005

Effective Date: 01Apr2018

Adapted Mayo Score	Clinical Remission Rate	0.1mg QD	Placebo	ANCOVA	Week 12	FAS, mFAS, PPS	NRI
Complete Mayo Score	Clinical Remission Rate	0.2mg QD	Placebo	ANCOVA	Week 12	FAS, mFAS, PPS	NRI
Complete Mayo Score	Clinical Remission Rate	0.1mg QD	Placebo	ANCOVA	Week 12	FAS, mFAS, PPS	NRI
Mayo Endoscopic Subscore	Mucosal Healing Rate	0.2mg QD	Placebo	ANCOVA	Week 12	FAS, mFAS, PPS	NRI
Mayo Endoscopic Subscore	Mucosal Healing Rate	0.1mg QD	Placebo	ANCOVA	Week 12	FAS, mFAS, PPS	NRI
Exploratory Endpoints (Stage 1)							
IBDQ	Change from Baseline	0.2mg QD	Placebo	ANCOVA	Week 12	FAS, mFAS	MCMC MI, LOCF
IBDQ	Change from Baseline	0.1mg QD	Placebo	ANCOVA	Week 12	FAS, mFAS	MCMC MI, LOCF

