9.8.2.2 Analysis for secondary study endpoints

For all categorical secondary efficacy endpoints, their statistical summaries need to be made based on the treatment group: number of cases, percentage, and 95% confidence interval. The stratified Cochran-Mantel-Haenszel (CMH) χ^2 test will be used with a 95% confidence interval for the difference in each category of rates.

For the quantitative secondary efficacy endpoints, the statistical method is similar to that for primary efficacy endpoint.

All secondary efficacy analyses will be performed between treatment groups (0.2 mg, 0.1 mg) and placebo and based on FAS and PPS. All results of these comparative analyses are used for exploratory purpose. More details of analyses are provided in the SAP.

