14.2.3. MISSING IMPUTATION FOR PRIMARY EFFICACY

Multiple Imputation

Multiple imputation has 3 distinct phases: Imputation, Analysis and Combining. During the Imputation Phase, the missing data values are filled-in to form a complete dataset. This is done 'm' times. For the Analysis Phase, each of the 'm' complete datasets are analysed by a statistical

Document: Statistical Analysis Plan

Author: [name]

Version Number: 1.1

Version Date: 18Jan2023

Template No.: CS_TP_BS016 Revision 5

Reference: CS_WI_BS005

Effective Date: 01Apr2018

model (as specified in Section 14.2.2). The Combining Phase pools the parameter estimates with their standard errors across the ‘m’ complete datasets and produces an average estimate with a standard error calculated using Rubin’s formula this allows for the uncertainty between imputations as well as the variability within each analysis.

Multiple imputation assumes that the data are missing at random (MAR). MAR assumes that the missingness does not depend on the actual missing values, but that the missing data can be completely explained by the observed data. To test the robustness of the multiple imputation strategy a tipping point analysis may be implemented.

In the case of mayo scores, a multiple imputation approach is implemented for the missing individual adapted mayo score.

Each individual mayo score is imputed and then the composite endpoint measures are created (see list of endpoints in APPENDIX 2).

There are 4 steps to this process:

1. Create a dataset with one record per subject, containing all values of each mayo score for all visits (baseline and week 12 on one record) in stage 1. These variables are included because they are correlated with the endpoint and/or missingness. The multiple imputation process creates complete datasets using PROC MI in SAS 9.4. During post-processing, the endpoints are derived in each of the complete datasets. The endpoints and analysis model in APPENDIX 2.
2. Run ‘m’ times Markov Chain Monte Carlo (MCMC) imputations to make the missing values in the dataset have a full missingness pattern. This will produce a dataset with an index variable _imputation_ and otherwise the same variables as the input dataset. It will have one record per imputation per subject.

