14.3.3. ANALYSIS OF SECONDARY EFFICACY VARIABLES

Unless otherwise specified, all secondary efficacy analyses will be performed between treatment group and placebo and based on FAS and PPS. All results of these comparative analyses are used for exploratory purpose.

The clinical response rate at week 12, clinical remission rate at week 12, and mucosal healing rate at week 12 will be analysed

Summary statistics of qualitative statistic will be provided by each treatment group. Statistical comparison between the 0.2 mg CBP-307 group versus the placebo group and between 0.1 mg versus placebo group will be conducted using the Cochran Mantel Haenszel (CMH) test, stratified by whether treatment with a tumor necrosis factor (TNF)- α antagonist failed (Yes or No). The p-value on the rate difference and the 95% Newcombe confidence interval (CI) will be provided.

For example:

The null hypothesis to be tested is that the clinical response rate at week 12 is not different between the 0.2 mg treatment group and the placebo treatment group; i.e.,

$$H_0: \text{clinical response rate at week 12}_{0.2 \text{ mg}} = \text{clinical response rate at week 12}_{\text{placebo}}$$

The alternative hypothesis is that clinical response rate at week 12 in the 0.2 mg treatment group is higher than that of the placebo treatment group, i.e.,

$$H_A: \text{clinical response rate at week 12}_{0.2 \text{ mg}} \neq \text{clinical response rate at week 12}_{\text{placebo}}$$

Document: Statistical Analysis Plan

Author: [name]

Version Number: 1.1

Version Date: 18Jan2023

Template No.: CS_TP_BS016 Revision 5

Reference: CS_WI_BS005

Effective Date: 01Apr2018

for quantitative summary statistics, the least square mean (LSMEANS), together with the p values and the 95% confidence intervals, between 0.2 mg vs. placebo and between 0.1 mg vs. placebo will be reported using the ANCOVA model (SAS PROC MIXED), with the stratification factor as the confounding factor in the ANCOVA model and the baseline values as covariate.

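### SAP Appendix 2 lists ANCOVA for all ten binary secondary comparisons, where SAP 14.3.3 and protocol 9.8.2.2 specify a stratified CMH test

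*SAP*

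**What the plan says.** **SAP Appendix 2.** The table has a "Statistical Method" column, and every row reads ANCOVA. That includes the rows labelled "Clinical Response Rate", "Clinical Remission Rate" and "Mucosal Healing Rate". All of these are yes/no outcomes, and all carry non-responder imputation in the last column.

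**SAP 14.3.3.** The text names the same three outcomes: "The clinical response rate at week 12, clinical remission rate at week 12, and mucosal healing rate at week 12 will be analysed". The comparison, for each dose against placebo, "will be conducted using the Cochran Mantel Haenszel (CMH) test, stratified by whether treatment with a tumor necrosis factor" antagonist therapy failed. The interval is a 95% Newcombe interval. ANCOVA appears later in the same section and is confined to the quantitative endpoints.

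**Protocol 9.8.2.2.** For all categorical secondary endpoints the sentence on the test opens "The stratified Cochran-Mantel-Haenszel (CMH". It calls for that chi-square test together with a 95% confidence interval for the difference in rates.

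**SAP 3.3.** Four changes from the protocol are listed: the mFAS, multiple imputation, an added remission definition and an all-stages 0.2 mg analysis. A change from CMH to ANCOVA is not among them.

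**SAP 14.2.3.** The multiple-imputation text sends the reader to the table: "The endpoints and analysis model in APPENDIX 2".

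**The concern.** Appendix 2 is the only place in the SAP that sets out endpoint, comparison, method, population and imputation row by row, so a programmer may well build the outputs from it. Followed literally, it yields least-squares mean differences from a linear model on a 0/1 outcome. Followed from 14.3.3, the same endpoint yields a stratified CMH p-value and a rate difference with a Newcombe interval. The SAP has no rule saying whether body or appendix prevails.

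Response, remission and healing rates are the content of the first secondary objective (SAP 2.2), so they will be read closely even though they are exploratory. SAP 14.4.2 also makes the sub-study 1 rate analyses in stage 2 the same as the stage 1 secondary analyses, so the ambiguity carries forward.

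**Working it through.** **1. The arm size used below.** The plan's own figure is 52 per arm (protocol 9.2, SAP 7.4), from a difference of 1.2, SD 2.0, two-sided alpha 0.05, power 80% and 15% dropout.

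- n per arm = 2 × (1.960 + 0.842)² × 2.0² / 1.2² = 43.6, so 44.
- 44 / 0.85 = 51.8, so 52.

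The stated figure reproduces. It serves only as the arm size in step 4; the contradiction does not depend on it.

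**2. Count of the rows in Appendix 2.**

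| Outcome | Score | Rows (0.2 mg, 0.1 mg) | Method in Appendix 2 | Method in 14.3.3 and protocol 9.8.2.2 |
|---|---|---|---|---|
| Clinical response | Adapted Mayo | 2 | ANCOVA | Stratified CMH |
| Clinical response | Complete Mayo | 2 | ANCOVA | Stratified CMH |
| Clinical remission | Adapted Mayo | 2 | ANCOVA | Stratified CMH |
| Clinical remission | Complete Mayo | 2 | ANCOVA | Stratified CMH |
| Mucosal healing | Endoscopic subscore | 2 | ANCOVA | Stratified CMH |

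Total: 2 + 2 + 2 + 2 + 2 = 10 rows. All ten read ANCOVA and none reads CMH. Each row carries its own entry between the comparator and the visit, so the broken table header in the extracted text does not explain it. The added exploratory remission rate (SAP 3.3 and 14.4.1) is also binary but has no row in Appendix 2, so ten is the full count.

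**3. What ANCOVA would mean for these rows.** The SAP's ANCOVA takes the baseline value of the endpoint as covariate. Eligibility (protocol 5.4.1, inclusion 4) requires an endoscopic subscore of at least 2, while healing and both secondary remission definitions rule out a subscore above 1. Every eligible subject is therefore unhealed and not in remission at baseline, and the covariate is constant. Response is defined by change from baseline and has no baseline value. The analyst would have to drop the covariate or choose another, such as the baseline Mayo score, which the SAP does not name for rates.

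**4. How often the two tests differ.** The documents give no rates for these endpoints, no stratum size and no prognostic effect of baseline, so all three are assumptions. Setting: 52 per arm, 25% in the TNF-failure stratum, true rates of 5% vs 20%, 10% vs 28% and 30% vs 55%, 4,000 trials per scenario.

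- CMH: χ² = [Σ(xₖ − n₁ₖrₖ/nₖ)]² / Σ[n₁ₖn₀ₖrₖ(nₖ − rₖ) / (nₖ²(nₖ − 1))], summed over the two strata. Here xₖ is responders on active, rₖ is all responders, and n₁ₖ, n₀ₖ and nₖ are the active, placebo and total numbers in stratum k.
- Linear model: response (0/1) = treatment + stratum, with or without a baseline covariate; t-test on treatment.
- Disagreement: exactly one of the two p-values is below 0.05.

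| Linear model | Assumed baseline log-odds effect per SD | Disagreement with CMH |
|---|---|---|
| No baseline covariate | – | 0.1-0.4% |
| With covariate | 0 | 2-3% |
| With covariate | 0.3 | about 3-4% |
| With covariate | 0.5 | 5-7% |
| With covariate | 0.8 | 8-11% |

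Across all simulations with a prognostic covariate, the top of the range was about 12%. Simulation error at a 5% rate is √(0.05 × 0.95 / 4,000) = 0.34 percentage points. Under no treatment effect (10% or 30% in both arms, baseline effect 0 to 0.5) disagreement was 0.1-1.7%.

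Five of the ten rows concern 0.1 mg, with about 30 subjects on that dose (protocol 9.2). These figures do not represent them.

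**The case against.** The strongest reply is that nobody would be misled. SAP 14.3.3 gives the test, the stratification factor, both comparisons, the hypotheses and the interval, and the protocol agrees. Against two concordant specifications, a repeated one-word cell looks like text copied down a column. The pointer in 14.2.3 sits in the multiple-imputation section, whereas the ten rows use non-responder imputation. Step 3 of that procedure takes its ANCOVA from 14.2.2, not from the table.

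Most of this stands, and it limits the point in three ways.

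- A reader might infer that the sponsor could pick the more favourable result afterwards. The documents do not support that: body and protocol both point to CMH, and nothing suggests a competing plan.
- A reader might infer that the pointer makes Appendix 2 the governing specification for these endpoints. It does not: 14.3.3 is the operative text for rates.
- A reader might blame the constant-variance assumption of a linear model on a 0/1 outcome. In the simulations that contributes very little, since without a baseline covariate the two tests almost always agree. The disagreement comes from baseline adjustment.

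What does not fall away is that the appendix states a method for ten comparisons that contradicts the SAP body and the protocol, in a table meant to be worked from.

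**Conclusion.** The contradiction is real and rests on the text alone: ten of ten binary rows in Appendix 2 carry a method that SAP 14.3.3 and protocol 9.8.2.2 do not prescribe and SAP 3.3 does not announce.

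Its reach is limited. Protocol 9.8.2.2 and 9.13 and SAP 14.3.3 make these comparisons exploratory, with no alpha attached. A reader might infer that the trial's main conclusion is at risk. It is not: the primary endpoint is a change score for which ANCOVA is the planned method in every place, and the sample size does not depend on the rates.

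For the 0.2 mg rows, disagreement on significance is under 0.5% of trials without a baseline covariate and roughly 2-12% with one. No single figure in that range should be quoted as the effect, because it moves with the assumed prognostic strength of baseline, and the rates and stratum size are assumptions too. Apart from significance, the form of the reported estimate and interval differs between the two methods. The correction is worth making before outputs are programmed from the table.

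**What to change.** In SAP Appendix 2, replace ANCOVA in the ten rate rows with: *CMH stratified by prior TNF-alpha antagonist failure; rate difference with 95% Newcombe CI (see 14.3.3)*. Naming the Newcombe interval matters, because an unspecified 95% interval would leave the table less exact than the body. Keep ANCOVA for the change-from-baseline rows only.

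The cost is a table correction in the SAP. It needs no new data or analysis and no change to the protocol.
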